4.4.1. Withdrawal from Study Drug

Due to the nature of treatment there will be no withdrawals from study drug.

4.4.2. Withdrawal from Trial

Reasons that a subject may discontinue participation in this study may include one of the following:

- Adverse event(s).
- Death.
- Subject withdrew consent.
- Physician decision.
- Lost to follow-up.

5. TREATMENT OF SUBJECTS

5.1. STUDY DRUGS

5.1.1. Raplixa

Table 1: Investigational Product

Product Name:	Raplixa™ [Fibrocaps™ (PRO-0601)]
Dosage Form:	Dry powder
Unit Dose	1.0 g/vial
Route of Administration	Topical
Physical Description	White to off-white powder
Manufacturer	Nova Laboratories, Ltd

Raplixa is a ready-to-use powder consisting of a blend of spray-dried human plasma-derived fibrinogen and thrombin particles with trehalose and calcium chloride with a concentration of 79 mg fibrinogen and 699 international units (IU) thrombin per gram Raplixa (1 vial).

The RaplixaSpray device is classified as a Class II device in the US. The device has been designed and manufactured according to International Organization for Standardization (ISO) 13485:2003 and 21 CFR 820 compliant processes to achieve simple, rapid delivery in the surgical environment onto a bleeding/oozing site. The device complies with the requirements of Medical Device Directive 93/43/EC as revised by 2007/42/EC for investigational devices. The delivery device uses a ball bearing mechanism to mobilize and subsequently deliver Raplixa via the outlet to the target site when the operating button is pressed. A part of this airflow is vented off through the back of the device, while the remaining airflow is used to deliver the Raplixa to the bleeding surface in a narrow plume. The device is supplied with two interchangeable nozzles: one rigid (attached to the device) and one flexible nozzle designed for use in hard to reach bleeding sites. The surgeon may switch the nozzles prior to or during use depending on the location of the bleeding site.

Raplixa Preparation

Prior to surgery, 2 vials of Raplixa and 2 to 3 gelatin sponges will be in the operating room. At sites using the RaplixaSpray device, 2 RaplixaSpray kits that contain the device, flexible nozzle and air filter, one regulator with a hose assembly with site specific connectors (both supplied by the Sponsor), and a central air supply or medical grade pressurized air will be available in the operating room. The second RaplixaSpray device is used as a back-up as needed.

The RaplixaSpray device will be connected to an air filter that is connected to a regulator set to a pressure of 1.5 bar (22 pounds per square inch [psi]), which is connected to either a central air supply or to a tank containing medical grade pressurized air. A vial of Raplixa will

be taken from the packaging in a sterile manner, then uncapped just prior to use and attached to the RaplixaSpray device by inverting the device and connecting the upright vial to the device. The device should be turned upright and the powder visualized in the well of the device prior to use. The application should start within 60 minutes after preparation.

For sites sprinkling Raplixa directly from the vial onto the TBS, the rubber stopper should be removed from the vial just prior to use to prevent the Raplixa from absorbing moisture from the air.

The gelatin sponges will be prepared according to the manufacturers' instructions.

Raplixa Administration

Two vials are allocated for each subject randomized to R+G. One vial (1.0 g) should be used for the initial treatment of the TBS regardless of the mode of administration used. The remaining one vial may be used as needed for the retreatment of the TBS that continues to bleed during the 5-minute TTH assessment period or, after hemostasis at the TBS has been achieved, applied to OBS that are part of the primary operative procedure. Importantly, all of the remaining Raplixa should not be used on OBS until after the 5-minute TTH assessment period has elapsed in order to ensure that adequate Raplixa is available for re-treatment of the TBS if required.

For treating large bleeding surface areas like those frequently encountered during liver and soft tissue surgical procedures, Raplixa is applied topically using the RaplixaSpray device as a thin layer of powder onto the bleeding surface. The device may be used at the discretion of the Investigator for small bleeding sites. The RaplixaSpray device should be held a minimum of 5 cm from the bleeding site when applying Raplixa by pushing the actuator button of the delivery device. Raplixa should be applied accurately and rapidly to the TBS. After Raplixa application, an absorbable gelatin sponge (dry or moistened) is applied, and held in place using light manual pressure with a sterile gauze sponge. Once hemostasis has been achieved, the gelatin sponge may be left in place with the excess carefully removed.

For smaller bleeding surface areas, Raplixa may be applied using the RaplixaSpray device or by sprinkling a thin layer of powder directly from the vial onto the TBS followed by an appropriately-sized gelatin sponge (dry or moistened) and light manual pressure with sterile gauze OR sprinkled directly from the vial onto an appropriately-sized, moistened gelatin sponge that is applied promptly to the TBS followed by light manual pressure applied with sterile gauze. This latter method of application is only appropriate for surgical procedures that have small bleeding surface areas. Once hemostasis has been achieved, the gelatin sponge may be left in place with the excess carefully removed.

The amount of Raplixa used (% of the vial contents) should be estimated and recorded on the eCRF.

5.1.2. Comparator

The control arm consists of Gelfoam® (Absorbable Gelatin Sponge, USP, Pfizer), an approved hemostatic device in the US and is the same as is used with Raplixa. Gelfoam will be provided to the US sites by the Sponsor; however, sites may use their own operating room supply of Gelfoam, if necessary, and must record the name, lot number, and expiration date. The gelatin sponge is cut to the appropriate size and applied topically, dry or moistened, according to the manufacturer's package insert, followed by manual pressure with sterile gauze. If possible, the gelatin sponge should be left in place, while the excess is removed from the bleeding site once hemostasis has been achieved. The appropriately-sized gelatin sponge may be moistened prior to application to the bleeding site, with moistened gelatin sponge recommended for irregularly-shaped bleeding areas. The gelatin sponge should be held in place with light manual pressure using sterile gauze, consistent with manufacturer's directions, and according to the protocol instructions. Subjects may be retreated with gelatin sponge as necessary during the 5-minute observation period. Once hemostasis has been achieved, the gelatin sponge may be left in place with the excess carefully removed.

5.2. PACKAGING AND LABELING

Study drug is provided by the Sponsor. Medication labels will comply with regulatory requirements. The storage conditions for each medication provided will be described on the medication label.

Raplixa raw materials, fibrinogen and thrombin, are supplied by CSL Behring. Raplixa is manufactured under aseptic conditions by Nova Laboratories, Ltd. and the final product labeled by [REDACTED], according to GMP requirements. Raplixa is packaged in 6 mL type I medical grade glass vials with white aluminum tear-off crimp caps (primary packaging) and a single foil pouch (secondary packaging).

The RaplixaSpray kit consists of a sterilized RaplixaSpray device with rigid nozzle, a sterilized flexible nozzle, and a sterile air filter, which is supplied separately from the Raplixa.

The gelatin sponges will remain in the original packaging labeled with the manufacturer's lot number, and an additional label specifying the clinical trial identification number and Sponsor.

5.3. STORAGE

Raplixa will be shipped to the pharmacy at each study site under controlled temperature with a temperature monitor. Upon receipt the shipment must be stored in a secured area at controlled room temperature (2°C–25°C). The RaplixaSpray kit will be shipped under ambient conditions. Upon receipt, the shipment should be stored in a secured area.

5.4. ACCOUNTABILITY

The Investigator or designee must maintain an inventory record of study drug received and all administered to assure the regulatory authorities and Sponsor that the investigational new drug will not be dispensed to any person who is not a subject under the terms or conditions set forth in this protocol.

The study drug supplied for use in this study is to be prescribed only by the Principal Investigator or designated sub-investigators and may not be used for any purpose other than that outlined in this protocol.

Study supplies will be shipped to the study site following receipt by the Sponsor or designee of written IRB approval and other appropriate study documentation as required.

Study drug and associated supplies are to be tracked and documented from the time of receipt at the site through subject dosing and return to the Sponsor or designee or destroyed at the site (as instructed by the Sponsor). All supplies, including partially used or empty vials, should be tracked. Accountability logs and specific instructions will be provided by the Sponsor or designee and should contain the identification of the subject to whom the drug was dispensed and the date, lot number and quantity of the drug dispensed to the subject. The site may use their own accountability form, if similar information is collected on their form.

All unused vials of study drug are to be retained at the site until inventoried by the Sponsor or designee. All vials used in the operating room may be destroyed, and should be documented. The Sponsor or designee will conduct drug accountability during the course of the study. Disposition of the used study drug during the course of the study should be handled according to the Sponsor's instructions and either disposed of, destroyed at the site, or returned to the Sponsor or designee. Appropriate site standard operating procedures will be followed for destruction of used study drug at the study site.

The Sponsor or designee will conduct final drug accountability at site closure. All used and unused study drug vials should be handled according to the Sponsor's instructions and either returned to the Sponsor or designee, or destroyed at the site.

In the event that study drug needs to be returned for any reason, the site will receive a written request listing the drug lot number(s) to be returned and the reason for the return request.

5.5. CONCOMITANT MEDICATIONS

Subjects may continue all normally prescribed medication regimens during this trial, and must notify the investigator when changes are made to their medication regimens. Medications will be coded using the WHO drug dictionary.

5.5.1. **Rescue Treatment**

If hemostasis is not achieved TBS during the 5-minute TTH assessment period, administration of additional study drug (no more than 2 vials of Raplixa [2.0 g] total), or other topical hemostats are permitted. If hemostasis cannot be achieved at an OBS or Raplixa is not indicated for use at the OBS, rescue treatment, if needed, should follow a tiered approach:

1. Additional study drug or surgical hemostatic measures (e.g., suture, cautery, and ligature) should be considered first.
2. Followed by thrombin-free topical hemostats.
3. Finally, thrombin-containing hemostats (recombinant or human plasma-derived products) may be administered, if needed.

A list of examples of thrombin-free and thrombin-containing hemostatic agents is provided in Table 2.

Table 2: Examples of Other Topical Hemostatic Agents

Thrombin-Free	Thrombin-Containing ^a
CoSeal™	CoStasis®/Vitage®/TM
Surgifoam™	Crosseal™
Ultrafoam™	Tisseel®
Gelfoam®	Fibrin sealant produced by the blood bank or in the operating room
Instat™	Evicle™
BioGlue®	Evithrom™
DuraSeal®	Recothrom®
Bone wax®	Surgiflo®
	Tachosil®
	Artiss®

a. Investigators should consider the use of products containing thrombin, only after other rescue alternatives fail.

5.6. **BLINDING**

Subjects will be randomized in a single-blinded manner. Randomization will be done in a 2:1 ratio (active:control).

5.6.1. **Blinding of Study Medications**

Study drugs will be blinded to study subjects but not to the Investigators, the study site personnel, or the Sponsor's study team.

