target and non-target bleeding sites). Rescue treatment may be administered if necessary in a tiered approach at the TBS or other bleeding sites (OBS) with thrombin-containing hemostats permitted after all other treatment options have been attempted after the TTH assessment period has elapsed, at the discretion of the Investigator.

For subjects randomized to Raplixa, at any time after hemostasis has been achieved at the TBS, and the 5-minute TTH assessment period has elapsed, the remaining Raplixa may be used at additional appropriate OBS that are part of the primary surgical procedure. Importantly, the remaining Raplixa should not be used on OBS until after the 5-minute TTH assessment period has elapsed in order to ensure that adequate Raplixa is available to use in the event of re-bleeding from the TBS. The amount of Raplixa applied and the incidence of hemostasis achieved at OBS will be recorded; however, the primary efficacy analysis will not include hemostasis data from the OBS.

Subjects will undergo a safety evaluation consisting of a targeted physical examination and clinical laboratory tests on Day 2 (Visit 3). If the subject's surgery was performed as an outpatient procedure, the Visit 3 assessment may be conducted over the phone with the physical examination conducted and laboratory tests collected prior to discharge on Day 1. Safety evaluations will also be performed on Day 7 (Visit 4) via telephone, if the subject has been discharged, and on Day 30 (Visit 5; End of Study Visit). Immunogenicity samples (monitoring for anti-thrombin antibodies) will be collected and analyzed at baseline and at Day 30 for all treated subjects, except subjects who are less than 6 months old. Additional monitoring for anti-fibrinogen antibodies will be limited to subjects found positive for anti-thrombin antibodies and subjects with unexplained bleeding or clinical suspicion of bleeding related to antibody formation.

Number of Subjects:

The study will enroll a total of up to 87 subjects.

Diagnosis and Main Criteria for Selection:

The study will enroll subjects undergoing one of the following surgical procedures:

1. Hepatic Surgery

Hepatic wedge resection or anatomic resection of 1 to 5 contiguous hepatic segments, which may be combined with surgical procedures involving the pancreas, gall bladder, bile duct or intestines. Subjects undergoing living-related liver donation are also eligible.

2. Renal Surgery

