During a surgical procedure on Day 1 (Visit 2), subjects will be initially treated with up to one vial of Raplixa (1.0 g) plus gelatin sponge or gelatin sponge alone at the TBS. The TTH will be assessed every 30 seconds for up to 5 minutes. Bleeding appropriate for TTH evaluation is defined as mild to moderate bleeding, either on its own or remaining after brisk/severe bleeding has been controlled by standard surgical modalities. Subjects may be retreated with their assigned treatment as necessary during the 5-minute TTH assessment period, with up to a maximum of 2 vials of Raplixa (2.0 g) in total (for target and non-target bleeding sites). Rescue treatment may be administered at the TBS or OBS if necessary in a

tiered approach after the 5-minute TTH assessment period has elapsed, at the discretion of the Investigator (see Section 5.5 for details).

[figure not shown]
For subjects who are randomized and receive Raplixa, at any time after hemostasis has been achieved at the TBS and the 5-minute TTH assessment period has elapsed, the remaining Raplixa may be used at additional appropriate OBS that are part of the primary surgical procedure. Importantly, the remaining Raplixa should not be used on OBS until after the 5-minute TTH assessment period has elapsed in order to ensure that adequate Raplixa is available to use in the event of re-bleeding from the TBS. The amount of Raplixa applied and the incidence of hemostasis achieved at OBS will be recorded; however, the primary efficacy analysis will not include hemostasis data from the OBS.

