7.2. ASSESSMENT OF EFFICACY

7.2.1. Time to Hemostasis (TTH)

A TBS with mild to moderate bleeding and a surface area of $\leq 100 \text{ cm}^2$ will be identified, treated according to the assigned study drug, and used to measure TTH. Study drug should be applied as rapidly as possible to the TBS.

The measurement of TTH will begin at $t=0$, which is the time R+G study drug application to the TBS is started and will end when hemostasis has been achieved or the 5-minute TTH assessment period ends. If hemostasis has not been achieved within 5 minutes, the subject will be considered a treatment failure and the surgeon will implement additional hemostatic measures, including surgical interventions or the use of alternative topical hemostatic agents or devices. See Section 5.5 for a list of example rescue treatments.

TTH will not be measured at OBS treated with study drug, but whether or not hemostasis was achieved and the approximate amount of study drug used will be recorded as described above.

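### Tiered rescue covers the target bleeding site in the synopsis and Section 3.1 but not in Section 5.5.1, and the step left open affects a secondary endpoint

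*Combined protocol and SAP*

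**What the plan says.** Four places in the protocol deal with rescue at the TBS.

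- **Synopsis, Methodology:** "Rescue treatment may be administered if necessary in a tiered approach at the TBS or other bleeding sites (OBS". It puts thrombin-containing hemostats after all other options and leaves the decision to the investigator.
- **Section 3.1:** "Rescue treatment may be administered at the TBS or OBS if necessary in a" tiered approach once the 5-minute period for assessing time to hemostasis (TTH) is over. This is also at the investigator's discretion, with a cross-reference to Section 5.5 for details.
- **Section 5.5.1:** the two kinds of site are separated. If the TBS is still bleeding after the 5-minute period, additional study drug (within the two-vial limit) "or other topical hemostats are permitted". The numbered tiers are introduced by the next sentence, which begins "If hemostasis cannot be achieved at an OBS or Raplixa is not indicated for use at the OBS, rescue treatment, if needed, should follow". The first tier reads "Additional study drug or surgical hemostatic measures (e.g., suture, cautery, and ligature) should be considered first". Thrombin-free topical hemostats are second and thrombin-containing products third. Footnote a to Table 2, which names no site, reserves thrombin-containing products until the other rescue options have failed.
- **Section 7.2.1:** for a TBS not controlled in 5 minutes, "the surgeon will implement additional hemostatic measures, including surgical interventions or the use of alternative topical hemostatic agents or devices". It gives no order and cites Section 5.5 only for examples.

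Sections 3.3 and 10.4.4.2 make the use of alternative hemostatic agents on the TBS, through Visit 5, a secondary efficacy endpoint. Section 10.4.4.2 leaves its analysis to the SAP. Section 5.6.1 states that investigators and site staff are not blinded.

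**The concern.** A surgeon who follows the cross-reference in Section 3.1 reaches a tier list whose opening sentence covers only OBS. The sentence that does cover the TBS gives a choice without an order and does not mention surgical measures.

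This matters because the endpoint counts an agent, not a bleeding outcome. If persistent TBS bleeding is stopped with more study drug or with suture, cautery or ligature, and no other agent is used there later, the subject does not count. If the surgeon goes straight to a thrombin-free topical hemostat, the subject counts. The protocol's statements on the TBS do not agree on whether the first course should be considered before the second. The person choosing knows the assigned arm, so the two arms could be handled differently under the same text. The treatment comparison on this endpoint would then partly reflect how the rescue text was read.

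**Working it through.** **Step 1. Compare the passages on one question: at the TBS, do study drug or surgical measures come before another topical hemostat?**

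- Synopsis: tiered at the TBS, but only the last tier (thrombin-containing products) is spelled out.
- Section 3.1: tiered at the TBS, with Section 5.5 to supply the tiers. The only tiers there put study drug or surgical measures first, so on this route the answer is yes.
- Section 5.5.1, sentence on the TBS: study drug or other topical hemostats, with no order. The answer is no stated precedence.
- Section 5.5.1, tier list: yes, but under a sentence limited to OBS.
- Section 7.2.1: silent on order.

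The direct conflict is between the synopsis and Section 3.1 on one side and Section 5.5.1 on the other. Section 7.2.1 does not contradict either.

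**Step 2. Ask the same question about thrombin-containing products.** The synopsis puts them last, and footnote a to Table 2 puts them last without limiting the site. There is no conflict on that step. The open step is only the one in Step 1, for thrombin-free agents.

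**Step 3. Reproduce the plan's own figure, to confirm the rates used for scale.** Inputs from Section 10.1: 87% (R+G, n = 58), 60% (G, n = 29), two-sided 0.05, chi-square test.

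- Pooled proportion: (2 × 0.87 + 0.60)/3 = 0.78
- Standard error under no difference: √[0.78 × 0.22 × (1/58 + 1/29)] = 0.0942
- Standard error under the alternative: √[0.60 × 0.40/29 + 0.87 × 0.13/58] = 0.1011
- Power: Φ[(0.27 − 1.96 × 0.0942)/0.1011] = Φ(0.844) = 0.80

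The stated power of about 80% with 87 subjects is reproduced and is not in dispute.

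**Step 4. Bound the number of subjects concerned.** Expected subjects without hemostasis at 4 minutes:

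- G: 0.40 × 29 = 11.6
- R+G: 0.13 × 58 = 7.5
- Total: 19.1 of 87

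Rescue starts after 5 minutes. Some of these subjects will reach hemostasis between 4 and 5 minutes, and Section 10.1 gives no 5-minute rate. The counts are therefore an approximate upper bound on subjects needing rescue for failure at 5 minutes.

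**Step 5. See what an endpoint rate would require.** In each arm, the rate equals the proportion still bleeding at 5 minutes times the share of those who receive an alternative agent, plus any first use of such an agent on the TBS later, up to Visit 5. The protocol gives none of these three quantities, so Step 4 bounds the subjects exposed to the ambiguity but does not give the endpoint rate.

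**The case against.** The strongest reply is that little turns on the mismatch. Section 3.1 names Section 5.5 as the operative text, so there is one place to look. The synopsis could be read as asking only that thrombin-containing products come last, which footnote a already secures. The tiered text is itself soft: it leaves rescue to the investigator's discretion, and its first tier says only what to consider first. Any dependence on the surgeon comes mainly from the openly stated single-blind design and would largely survive a redraft. Finally, the SAP to which the analysis is deferred may define the endpoint more tightly.

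Much of this stands, and it limits the point. Reconciliation would reduce surgeon dependence, not remove it. A separate SAP is not in the supplied text, so its endpoint definition cannot be judged. But the reply does not remove the conflict: Section 3.1 sends the reader to Section 5.5 for a tiered approach at the TBS, and the tiers found there are introduced for OBS only.

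A reader might infer three stronger things that the documents do not support.

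- **That early thrombin use would distort the antibody comparison.** Footnote a keeps thrombin-containing products last at the TBS too, and the tiered rule also allows them as a final step.
- **That subjects who reach the first tier drop out of the endpoint under one rule.** A subject in whom that step fails can still receive another agent and count. A subject controlled by study drug or surgery alone does not count under either reading.
- **That the endpoint could run from about zero up to the 4-minute failure rates of 13% and 40%.** The lower end assumes that the first step always works. The upper end assumes that every 4-minute failure is still bleeding at 5 minutes and is given another agent. The protocol supplies neither assumption, and later use through Visit 5 also counts.

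**Conclusion.** The point holds in a limited form. The synopsis and Section 3.1 conflict with Section 5.5.1 on whether the tiered approach governs rescue at the TBS. The unresolved step is whether study drug or surgical measures precede a thrombin-free topical hemostat there. It bears on one secondary endpoint, with an unblinded surgeon making the choice. The 4-minute primary endpoint is not affected, because this rescue text applies after the 5-minute period.

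By the planning rates, at most about 11.6 of 29 G and 7.5 of 58 R+G subjects would need rescue for failure at 5 minutes. This rests on the Section 10.1 rates holding and on failures at 5 minutes not exceeding those at 4. The size of any shift in the endpoint, or of any difference in handling between arms, cannot be calculated from the documents. The inconsistency should be corrected because the remedy is cheap. It does not undermine the trial's main comparison.

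**What to change.** Reconcile the synopsis, Section 3.1 and Section 5.5.1, and align Section 7.2.1 with them, so that a single rescue rule for the TBS is stated and applies identically in both arms. Which rule that is should be decided by the sponsor's clinical team.

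Two additions would help the analysis whichever rule is chosen. First, state in the endpoint definition what counts as an alternative agent. Table 2 lists Gelfoam among other topical agents although gelatin sponge is study treatment in both arms, and the supplied text does not say whether its re-use counts. Second, record the sequence of rescue measures at the TBS, so that the endpoint can be read against what was tried first in each arm.

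The core change costs protocol wording and a site clarification. The additions need a line in the endpoint definition and, if the sequence is not already captured, a field on the case report form. Sample size and the primary analysis are unchanged.
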